10.2 PET Scans

Visual assessment currently is considered adequate for determining whether a PET scan is positive. A Deauville score should be reported. In brief, a positive scan is defined as focal or diffuse FDG uptake above background in a location incompatible with normal anatomy or physiology.

10.3 Response Criteria

For measurement of response, standard 2014 criteria as described in “Recommendations for Initial Evaluation, Staging, and Response Assessment of Hodgkin and Non-Hodgkin Lymphoma: The Lugano Classification” will be used (see Appendix D) [20].

10.4 If a subject who had radiological evidence of PD is clinically stable or improving or exhibiting signs of tumor flare without confirmation of PD by PET or biopsy, the subject may continue treatment with ibrutinib upon approval by the sponsor-investigator.. If tumor flare is suspected, the PI may continue ibrutinib and obtain additional radiological and clinical evaluation at a subsequent disease evaluation visit within 6 weeks, with a determination as to whether ibrutinib should be discontinued (in subjects with evidence of further progression at repeat evaluation) or further treatment provided (in subjects with signs of subsequent tumor shrinkage or stable disease without clinical deterioration).

10.5 Progression-free survival (PFS): PFS will be measured as time from first study drug administration to the first occurrence of disease progression or death from any cause. Data for subjects without disease progression or death will be censored at the date of the last tumor assessment and before the initiation of alternative

anticancer therapy. The estimates will be formed using the all treated population. Progression-free survival will be calculated using assessments by investigators. Kaplan-Meier methodology will be used to estimate event-free curves and corresponding quartiles (including the median).

10.6 Assessment inadequate, objective status unknown: Progression has not been documented and one or more target lesions or other sites of disease have not been assessed or inconsistent methods of assessment were used.

10.7 Bone Marrow Status: Bone marrow status is evaluated as follows:

Positive: Unequivocal cytological or architectural evidence of malignancy.

Negative: No aggregates or only a few well-circumscribed lymphoid aggregates.

Indeterminate: Does not qualify for either Positive or Negative Status. *Note this typically consists of increased number or size of aggregates without cytological or architectural atypia.

11.0 STATISTICAL CONSIDERATIONS

11.1 The primary objective is to gain a preliminary (pilot) assessment of the efficacy of this regimen based on overall response rate (ORR) (see section 10.2). Analyses of secondary endpoints will be primarily descriptive. Patients with R/R TIL have a poor prognosis and short median survival; therefore an ORR of $\geq 30\%$, a disease control rate of $\geq 50\%$ (defined as ORR plus stable disease, as defined in section 10.2), or a median PFS of ≥ 6 months will be considered a success.

11.2 Anticipated accrual: We anticipate that accrual will take 1-2 years.

11.3 Estimated* distribution of study population by gender and race and ethnicity:

Ethnic Category	Females	Males
American Indian/Alaska Native		
Asian	1	1
Native Hawaiian or Other Pacific Islander		
Black or African American	1	1
White	8	8
More than one race		
Unknown or not reported		
Racial Categories: Total of all subjects	10	10

*The exact sample size is not known since it is dependent on the number of evaluable patients, but we estimate the total enrollment will be 20.

11.4 If treatment efficacy meets predefined success rate of 30% overall response rate (combined CR + PR) then a recommendation may be made to expand the study to accrue an additional 20 patients.

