5.1.8.3 Creatinine clearance (Clcr) $> 25 \text{ mL/min}$

5.1.9 Patients must be anticipated to complete 2 cycles of therapy in the opinion of the treating physician.

5.1.10 Women of childbearing potential and men who are sexually active must affirm they are practicing a highly effective method of birth control during and after the study consistent with local regulations regarding the use of birth control methods for subjects participating in clinical trials. Men must agree to not donate sperm during or after the study. For females, these restrictions apply for 1 month after the last dose of study drug. For males, these restrictions apply for 3 months after the last dose of the study drug.

5.1.11 Women of childbearing potential must have a negative serum (beta-human chorionic gonadotropin [β -hCG]) or urine pregnancy test at Screening. Women who are pregnant or breastfeeding are ineligible for this study.

5.1.12 Sign (or their legally-acceptable representatives must sign) an informed consent document in accordance with institutional and federal guidelines indicating that they understand the investigational nature of and procedures required for the study, including biomarkers, and are willing to participate in and comply with the guidelines of the study.

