9.0 STUDY CALENDAR

Required Studies	Screening (within 4 weeks of initiation of treatment)	During treatment	Post Therapy	Follow-up
Physical				
Medical History	X			
Physical Exam	X	X ⁴	X ⁶	X ⁷
Performance Status	X	X ⁴	X ⁶	
Clinical Disease Assessment	X	X ⁴	X ⁶	
Adverse Event Assessment	X	X ⁴	X ⁶	
EKG	X			
Lab				
CBC and differential	X	X ⁴	X ⁶	
Serum creatinine, total bilirubin, SGOT (AST), electrolytes, glucose	X	X ⁴	X ⁶	
Albumin, LDH	X		X ⁶	
Bone marrow studies	X ¹	X ¹		
Pregnancy test	X ²			
Pathologic studies	X			
Radiology				
CT (preferred) or MRI Chest, abdomen and pelvis	X	X ⁵	X ⁶	
FDG-PET (skull base to proximal femur)	X ³	X ⁵		

¹ Bone marrow studies include aspirate and unilateral or bilateral biopsy and should be performed at screening unless approved by the Sponsor-Investigator or Lead Sub-Investigator. If all bone marrow studies are negative at screening, these do not need to be repeated. If bone marrow status is unknown or positive at screening, patients will need to have a bone marrow study to confirm a suspected CR.

² Pregnancy test is only required in women of childbearing potential.

³ May be obtained up to 8 weeks in advance of initiation of therapy (provided no additional anti-cancer therapies are administered during the interval). A Deauville score should be assigned [19].

⁴ At the beginning of therapy (within 3 days), on completion of every cycle (+/- 3 days) during first 9 cycles, then on completion of every 4 cycles (+/- 6 days) thereafter. For the first day of therapy, pre-entry H&P, PS, disease assessment, and adverse event assessment may be used (these do not need to be repeated within 3 days) and labs done within 14 days are acceptable.

⁵ During treatment restaging CT (preferred) or MRI will be performed on completion of every 3 cycles of therapy (+/- 6 days) during the first 9 cycles and on completion of every 8 cycles of therapy (+/- 12 days) thereafter, or as indicated to evaluate clinical suspicion of disease progression. Restaging PET/CT will be performed once during therapy on completion of the first 6 cycles (+/- 6 days). A Deauville score should be assigned [19] when restaging PET is performed.

⁶ Post therapy studies should be done within 28 days after the last dose of ibrutinib. A CT (preferred) or MRI will be obtained if prior imaging was > 21 days of therapy's completion.

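### Does the undefined term 'evaluable' in 11.3 leave the 30% response-rate bar without a fixed denominator?

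*Combined protocol and SAP*

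**What the plan says.** Section 11.1 calls the study a pilot assessment of efficacy based on ORR. It counts any one of three results as success: ORR of at least 30%, disease control rate (DCR) of at least 50%, or median PFS of at least 6 months. No denominator is given for ORR or DCR.

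The footnote to the accrual table in 11.3 reads "The exact sample size is not known since it is dependent on the number of evaluable patients", and continues "but we estimate the total enrollment will be 20". 'Evaluable' is not defined there or elsewhere.

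Section 11.4 says that if ORR reaches 30%, "then a recommendation may be made to expand the study to accrue an additional 20 patients".

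Section 10.5 names a population, for PFS: "The estimates will be formed using the all treated population". Section 10.6 defines a status for inadequate assessment. It applies only when progression has not been documented, and the section does not say whether such patients stay in the ORR or DCR denominator.

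**The concern.** ORR is the primary endpoint, and reaching 30% both counts as success and opens the way to 20 more patients. With about 20 patients, one or two can decide the result. If the denominator is settled after the data are seen, patients who die or decline before imaging could be left out. They are mostly failures, so leaving them out would raise the rate.

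The calendar makes such patients plausible. Entry requires only that "Patients must be anticipated to complete 2 cycles of therapy in the opinion of the treating physician", which is 6 weeks, whereas "During treatment restaging CT (preferred) or MRI will be performed on completion of every 3 cycles of therapy", so the first scheduled scan falls at about week 9. PFS is tied to all treated patients, so the three routes to success could also end up describing different groups.

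**Working it through.** **Inputs from the document.** Bars of 30% ORR and 50% DCR (11.1, 11.4). Estimated enrolment 20 (11.3); the table agrees, 2 × (1 + 1 + 8) = 20. Cycle length 21 days (Schema). First restaging after 3 cycles (9.0, footnote 5). The 20 cannot be derived further, because no alpha, power or null rate is stated.

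**Inputs assumed.** True ORR 20%, true DCR 40%, and an unassessed share f of 5% to 20%, all of them failures. The document gives none of these.

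**1. Responders needed.** r(N) = 0.30 × N, rounded up.
- N = 20: 6.0, so 6.
- N = 19, 18, 17: 5.7, 5.4, 5.1, so still 6.
- N = 16: 4.8, so 5.
- N = 21: 6.3, so 7.

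**2. Can the same data give two verdicts with 20 treated?** Dropping 1, 2 or 3 patients leaves the requirement at 6, so nothing changes. Dropping 4 lets 5 responders pass: 5/20 = 25.0% fails, 5/16 = 31.25% passes. Four responders would need 7 exclusions (4/13 = 30.8%).

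**3. How likely is that?** Let K, the number unassessed, be Binomial(20, f), and let responders among the rest be Binomial(20 − K, 0.20/(1 − f)). The table gives the chance that the all-treated analysis fails while the evaluable-only analysis passes, with the same model for 21 treated.

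| f | 20 treated | 21 treated |
|---|---|---|
| 5% | 0.002 | 0.076 |
| 10% | 0.019 | 0.113 |
| 15% | 0.058 | 0.149 |
| 20% | 0.112 | 0.197 |

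With 21 treated, one exclusion is enough: 6/21 = 28.6% against 6/20 = 30.0%. That case arises if the 20 in 11.3 is overrun or is read as an evaluable target.

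**4. DCR with 20 treated.** Ten are needed. Two exclusions can change the verdict: 9/20 = 45% against 9/18 = 50%. By the same model the chance of passing rises from 0.245 (all treated) to 0.284, 0.360, 0.451 and 0.549 at the four shares. The differences are 0.040, 0.115, 0.206 and 0.305.

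**5. How large could the unassessed share be?** With exponential PFS at the plan's own 6-month bar, the proportion progressing or dying by day 63 is 1 − 2^(−63/182.6) = 0.213, or about 0.213 × 20 = 4.3 patients. At an assumed 3-month median it is 1 − 2^(−63/91.3) = 0.380, or 7.6 patients. These are early events, not unassessed patients. Clinical disease assessment is due "on completion of every cycle (+/- 3 days) during first 9 cycles", scans are allowed on suspicion of progression, and "Post therapy studies should be done within 28 days after the last dose of ibrutinib", with CT or MRI if the last imaging was more than 21 days before therapy ended. A patient with documented progression falls outside the 10.6 status and has a known outcome. Those left unassessed are mainly patients who die or withdraw with no post-baseline assessment.

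**6. Is an uncertain N itself a problem?** At a true ORR of 20%, the chance of reaching 30% runs from 0.089 (N = 24) to 0.196 (N = 20) over sizes 17 to 24. This is rounding in any percentage bar at small N. It compares trials of different sizes; once enrolment ends, N is known.

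**The case for a change.** The strongest case for a change is that 11.4 calls 30% predefined, and a percentage without a denominator is not fully predefined. The remedy would be a sentence or two, with no new data. The figures are not trivial everywhere: one patient suffices at 21 treated, two suffice for DCR, and DCR alone can make the study a success under 11.1. The reference in 11.1 to section 10.2 does not help, because 10.2 covers PET positivity; the response criteria are in 10.3 and Appendix D.

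It is true that no denominator is written down, and naming one would be tidier. But the case needs an evaluable-only response analysis, and the plan nowhere provides for one. The word appears once, in a note on how many patients will be enrolled. An all-treated analysis fits the text at least as well and matches 10.5. The larger effects come from the upper end of an assumed share and from treating every unassessed patient as a failure. The reference to 10.2 is a clerical slip that misleads nobody who reads on to 10.3.

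**Conclusion.** The concern describes missing detail, not a rule that gives a wrong answer. The sensible reading is all treated patients, with those lacking an adequate post-baseline assessment counted as non-responders. With 20 treated that means 6 responders are needed and 5 are too few.

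At that size the ORR verdict is unaffected by up to three exclusions. The chance of conflicting verdicts is 0.002 to 0.112, given a true ORR of 20% and 5% to 20% unassessed failures. It is higher at 21 treated and for DCR, under the same kind of assumption.

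The consequences are also limited. An ORR reversal alters success under 11.1 only if DCR and PFS both miss. Only 11.4 rests on ORR alone, and there the expansion is discretionary. No hypothesis test or error rate is stated, so none is breached. With about 20 patients, the report can show every patient's status and both rates. No change to the plan is called for.

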12.0 STUDY MONITORING AND REPORTING PROCEDURES

12.1 Adverse Event Reporting

Complete and timely reporting of adverse events (AEs) is required to ensure the safety of patients. Reporting requirements are determined by the characteristics of the adverse event including the *grade* (severity), the *relationship to the study therapy* (attribution), and the *prior experience* (expectedness) of the adverse event, and whether the event is *of interest* to Janssen Scientific Affairs. The guidelines outlined in this section, as well as the specific direction on each report form must be followed. The NCI Common Terminology Criteria for Adverse Events v4.0 (CTCAE) will be used to classify and grade toxicities.

12.2 Definitions and descriptions of terms used in adverse event reporting.

12.2.1 *Adverse Event (AE)*

An *adverse event* is defined as any unfavorable and unintended sign (including an abnormal laboratory finding), symptom, or disease temporally associated with the use of a medical treatment or procedure.

12.2.2 *Serious Adverse Event (SAE) or Adverse Drug Reaction (ADR)*

A *Serious Adverse Event* or *Adverse Drug Reaction* means any AE/ADR occurring at any dose that results in:

- Death;
- A life-threatening AE/ADR (i.e, the patient/subject was, in the view of the initial reporter/investigator, at immediate risk of death from the AE as it occurred. It does not refer to an AE that hypothetically might have caused death if more severe);
- Inpatient hospitalization or prolongation of existing hospitalization (i.e, hospitalization was required to treat or diagnose the AE/ADR: excludes hospitalization for unrelated reasons (e.g., social reasons such as pending placement in long-term care facility) OR surgery or procedure planned before entry into the study (must be documented in the CRF). Note: Hospitalizations that were planned before the signing of the ICF, and where the underlying condition for which the hospitalization was planned has not worsened, will not be considered serious adverse events. Any adverse event that results in a prolongation of the originally planned hospitalization is to be reported as a new serious adverse event;

- A persistent or significant disability or incapacity (disability here means that there is a substantial disruption of a person's ability to conduct normal life functions);
- A congenital anomaly/birth defect;
- An important medical event (i.e., AEs/ADRs that might not be immediately life-threatening, or result in death or hospitalization might be considered serious when, based upon appropriate medical and scientific judgment, they might jeopardize the patient/subject or might require medical or surgical intervention to prevent one of the other serious outcomes listed above);
- Any suspected transmission via a medicinal product of an infectious agent.

Sponsor-Investigator shall use his/her judgment to determine the relationship between the Serious Adverse Drug Experience and the Study Drug.

Disease progression should not be recorded as an adverse event or serious adverse event term; instead, signs and symptoms of clinical sequelae resulting from disease progression/lack of efficacy will be reported if they fulfill the serious adverse event definition.

12.2.3 Adverse Events of Special Interest

Specific adverse events or groups of adverse events will be followed as part of standard safety monitoring activities. These events will be reported to Janssen Scientific Affairs within 24 hours of awareness irrespective of seriousness (ie, serious and nonserious adverse events) following the procedure described above for serious adverse events and will require enhanced data collection. Specific adverse events of interest include:

1. Major Hemorrhage

Major hemorrhage is defined as any hemorrhagic event that is Grade 3 or greater in severity or that results in 1 of the following: intraocular bleeding causing loss of vision, the need for a transfusion of 2 or more units of red cells or an equivalent amount of whole blood, hospitalization, or prolongation of hospitalization.

2. Intracranial Hemorrhage

Any intracranial hemorrhage adverse event, including subdural hematoma/hemorrhage, epidural hematoma/hemorrhage and intracerebral hemorrhage, of any grade severity, will be captured as an event of special interest.

3. Other Malignancies

In addition to all routine AE reporting, all new malignant tumors, including solid tumors, skin malignancies and hematologic malignancies, are to be reported for

the duration of study treatment and during any protocol-specified follow-up periods including post-progression follow-up for overall survival.

12.2.4 *Pregnancy*

All initial reports of pregnancy must be reported to Janssen Scientific Affairs by the study-site personnel within 24 hours of their knowledge of the event.

Abnormal pregnancy outcomes (eg, spontaneous abortion, stillbirth, and congenital anomaly) are considered serious adverse events and must be reported as a Serious Adverse Event. Any subject who becomes pregnant during the study must discontinue further study treatment.

Because the effect of the study drug on sperm is unknown, pregnancies in partners of male subjects included in the study will be reported by the study-site personnel within 24 hours of their knowledge of the event.

Follow-up information regarding the outcome of the pregnancy and any postnatal sequelae in the infant will be required.

12.2.5 *Grade*

Grade is defined as the severity of the adverse event. The CTCAE Version 4.0 must be used to determine the grade of the adverse event. If toxicity is not listed in the CTCAE use the following general criteria for grading.

- 0 – No adverse event or within normal limits
- 1 – Mild adverse event
- 2 – Moderate adverse event
- 3 – Severe adverse event
- 4 – Life-threatening or disabling adverse event
- 5 – Fatal adverse event

12.2.6 *Attribution*

Attribution is defined as the determination of whether an adverse event is related to a medical treatment or procedure. Attribution categories are as follows:

- *Unrelated* The adverse event is *clearly NOT related* to therapy
- *Unlikely* The adverse event is *doubtfully related* to therapy
- *Possible* The adverse event *may be related* to therapy
- *Probable* The adverse event is *likely related* to therapy
- *Definite* The adverse event is *clearly related* to therapy

12.2.7 *Unexpected Adverse Event*

An adverse event is considered unlisted (unexpected) if the nature or severity is not consistent with the applicable product reference safety information. For ibrutinib, the expectedness of an adverse event will be determined by whether or not it is listed in the Investigator's Brochure and US package insert.

12.2.8 *Product Quality Complaint*

A product quality complaint may allege an injury or malfunction associated with the use of the drug product. It may involve the design, literature, packaging, advertising, availability, physical appearance or promotion of the drug product. It may also involve any discrete concern that questions the identity, quality, durability, reliability, safety, efficacy or intended performance of a drug product.

12.2.9 *J&J Medicinal Product*

J&J medicinal product includes the specific drug under study and other J&J medicinal product.

12.3 Routine Reporting

Routine reporting is required for all adverse events.

All applicable adverse events and special reporting situations, whether serious or non-serious, will be reported from the time a signed and dated ICF is obtained until 30 days following the last dose of study drug. Serious adverse events, including those spontaneously reported to the investigator within 30 days after the last dose of study drug, must be reported.

All events that meet the definition of a serious adverse event will be reported as serious adverse events, regardless of whether they are protocol-specific assessments.

All adverse events, regardless of seriousness, severity, or presumed relationship to study drug, must be recorded using medical terminology in the source document and the CRF. Whenever possible, diagnoses should be given when signs and symptoms are due to a common etiology (eg, cough, runny nose, sneezing, sore throat, and head congestion should be reported as "upper respiratory infection"). Investigators must record in the CRF their opinion concerning the relationship of the adverse event to study therapy. All measures required for adverse event management must be recorded in the source document.

The sponsor-investigator assumes responsibility for appropriate reporting of adverse events to the regulatory authorities. The sponsor will also report to Janssen Scientific Affairs all serious adverse events that are unlisted (unexpected) and associated with the use of the study drug. The sponsor must report these events to the appropriate IRB that approved the protocol unless otherwise required and documented by the IRB.

12.4 Expedited Reporting

All unexpected adverse events, serious adverse events, and adverse events of interest which may be due to study treatment or intervention, must be reported to the Sponsor-Investigator as soon as possible. Expedited reporting will be conducted

in accordance with FHCRC/Cancer Consortium IRB policies, applicable FDA regulations, and agreements with Janssen Scientific Affairs.

Expedited reporting additionally applies to any death occurring during protocol therapy or within 30 days of completing protocol therapy and any death that occurs more than 30 days after completing protocol treatment that is thought to be treatment-related and is not due to disease recurrence. Expedited reporting further applies to the occurrence of pregnancy or, new diagnosis of cancer during treatment or within 30 days of the last dose of study drug, or overdose of study drugs (regardless of adverse outcome).

